3.2 STUDY FLOWCHART

3.3 STUDY MATRIX

Time	Baseline	Week 4[^]
Informed Consent	X	
Inclusion/exclusion criteria	X	
Demographics	X	
Past Medical History	X	
Smoking history	X	
Blood pressure	X	X
*Pregnancy test (if appropriate)	X	
Flow Mediated Dilatation	X	X
Vascular Stiffness	X	X
Blood test	X	X
CO Breath test	X	X
[∞] Smoking Diary	X	X
Randomisation	X	
Training on use of EC (if allocated)	X	
Supply EC (if allocated)	X	
Serious Adverse Events		X
Adherence		X
Provision of smoking cessation support details		X

[^] The week 4 visit will be carried out at 4 weeks \pm up to 10 days.

* Urine pregnancy testing on females of childbearing potential who do not abstain from sexiary will be given out at baseline and collected at the 4 week visit

Patients will also be supported as required by regular phone or text to encourage adherence.

Participants who complete the study will receive a monetary incentive in the form of shopping vouchers. vouchers will be payable at the end of the study to the maximum value of £40. this incentive is purely for those who complete both visits as a way to try and minimise dropouts. this will only work if payment is made on completion of study. however if the study team have to withdraw a participants a £20 of shopping voucher could be paid per visit attended

4 STUDY POPULATION

4.1 NUMBER OF PARTICIPANTS

Number: 135 participants.

Recruitment period: 22 months

Dropout rate: it is anticipated that the dropout rates will vary depending on which group they have been randomised to. Assuming 10%, 15%, and 20% drop-out rates in the TC, EC-nicotine & EC-nicotine free groups respectively, we will require 135 participants to provide a final evaluable sample of 112 participants.

4.2 INCLUSION CRITERIA

- Aged 18 years and over
- Currently smoking ≥ 15 tobacco cigarettes per day for at least 2 years, or roll-up tobacco equivalent (cigar or pipe smokers will not be included).
- Willing to stop tobacco cigarettes for period of study if required
- Willing not to use electronic cigarettes if required
- Able to give informed consent

4.3 EXCLUSION CRITERIA

- Pregnant or lactating.
- Women of childbearing potential who do not abstain from sex or use effective contraception.
- On current prescribed medication for cardiovascular disease.
- History of cardiovascular disease (excluding hypertension), diabetes, active malignance or chronic renal disease.
- Nut allergy
- Participation in another clinical trial (other than observational trials and registries) with an investigational product and/or intervention within 30 days before visit 1.
- Use of electronic cigarettes within the last month.

Contraceptive advice to participants

Women of child-bearing potential, who do not abstain from sex, must be willing to have pregnancy testing prior to study entry. In addition, women of child bearing potential, who are sexually active, must be willing to use a form of a medically approved birth control method eg;

- Combined Oral Contraceptive Pill
- Placement of a intrauterine device - 'coil'
- Barrier methods of contraception: male condom only
- Established use of oral, injected, transdermal or implanted hormonal methods of contraception
- Male partner sterilisation (followed by the appropriate post-vasectomy documentation of the absence of sperm in the ejaculate).

5 PARTICIPANT SELECTION AND ENROLMENT

5.1 IDENTIFYING PARTICIPANTS

Participants will be recruited via a publicity campaign using a range of methods:

- Posters/leaflets distributed in various places which may include:
 - Football/Bingo halls/ Bowling
 - Smoking shelters
 - Pubs
 - Hospital main entrances/ hospital clinics
 - Shopping Centres/Supermarkets/Pubs/etc.
 - Benefits offices/Post offices etc.
 - Sheltered Housing /Housing Associations
 - Community and charitable outreach programs
 - GP waiting rooms
 - Local company newsletters/payslips
- Advertisements in local newspapers and on local radio stations.
- Social media including twitter and Facebook.
- Invitation to those eligible on registered research volunteer databases held by the research team and the Scottish Health Research Register (SHARE).
- Potential participants will be identified via the Scottish Primary Care Research Network (SPCRN).
- Existing data-bases of smokers where permission has been granted to be approached for research purposes

5.2 CONSENTING PARTICIPANTS

Obtaining consent will be carried out by the PI, researcher or other local delegated individual in accordance with TASC SOP07: Obtaining Informed Consent from Potential Participants in Clinical Research

Potential participants who have seen the publicity campaign will be invited to contact the study team via phone or email. The researcher or other delegated individual will discuss the study via a phone call and assess for suitability. If the participant is thought to be suitable a participant information sheet (PIS) will be posted to the participant and a baseline visit arranged, all participants will be given at least 24 hours to consider their participation. If they decide to participate, informed consent will be taken by the researcher or other delegated individual and eligibility by all the criteria confirmed.

Where a participant requests to speak with a physician from the study team the consent process will not be completed until the participant had spoken to the physician and had all their questions answered to their satisfaction.

5.3 SCREENING FOR ELIGIBILITY

Participants who contact the research team expressing their interest in the study will be contacted and their suitability will be assessed as above prior to consent and booking a screening visit. Eligibility will be confirmed with the participant during the screening visit. The study visits will be performed within the Division of

5.4 INELIGIBLE AND NON-RECRUITED PARTICIPANTS

The reason(s) for ineligibility will be explained to participants and any questions they have will be answered. They will be thanked for their participation and any relevant information from this will be added to their hospital notes and be communicated to their GP where the participant consents for this to happen.

5.5 RANDOMISATION

5.5.1 Randomisation

Randomisation will be carried out in a 1:1 fashion for the 2 randomised arms via a centrally controlled web-based GCP compliant randomisation system, TRUsT, run by Tayside Clinical Trials Unit (TCTU). To ensure balanced assignment across critical variables, a minimisation algorithm will be employed, using baseline age (≤ 40 years; > 40 years), sex (male; female) and smoking pack years (≤ 20 pack years; > 20 pack years). Randomisation will be performed by the PI, researcher or other local delegated individual.

Recruitment will stop when the required number is reached in each arm (maximum 45 per arm)

The TC arm will not be randomised.

To facilitate recruitment and minimise dropouts we propose to recruit the TC smoking arm as a separate non randomised group. Potential participants will be identified and approached in exactly the same ways as for the 2 EC arms. All participants will be asked if they wish to continue to smoke TC or to be randomised to one of the EC arms. This will enable us to recruit volunteers who would find it too difficult to stop their TC for 4 weeks. It will also avoid disappointment for those volunteers who are ready to stop smoking and do not wish to continue with their TC, which has the potential to lead to further dropouts. This is an unblinded study with the exception of the measurement of endothelial function and vascular stiffness which will be performed by a single blinded operator.

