2 STUDY OBJECTIVES & OUTCOMES

Table 1: Primary Objectives and Outcome Measures

Primary Objective	Outcome Measure	Timepoints measured
To determine the effect of EC-nicotine free on vascular function as compare to TC.	Change in FMD between the TC group and the EC-nicotine free groups	0 and 4 weeks

Table 2: Secondary Objectives and Outcome Measures

[figure not shown]
Secondary Objectives	Outcome Measures	Timepoints measured
To compare the effects of EC-nicotine vs EC-nicotine free on vascular function.	Change in FMD between EC-nicotine and EC-nicotine free groups	0 and 4 weeks
To compare the effects of EC-nicotine free vs TC on vascular function.	Change in Pulse Wave Velocity between the TC group and the EC-nicotine free groups. Change in Augmentation Index@75bpm between the TC group and the EC-nicotine free groups	0 and 4 weeks
To compare the effects of TC vs EC vs EC nicotine free on oxidative stress.	Change in total F2-Isoprostanes between the TC and EC groups	0 and 4 weeks

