5.5.2 Intervention Allocation

Participants will initially be asked if they wish to continue smoking TC or if they would like to be randomised to one of the EC arms. Participants who wish to be randomised to one of the EC arms will be randomised to one of two groups in a 1:1 fashion. The groups will be:

- a) Switch to electronic cigarettes containing nicotine plus flavour
- b) Switch to electronic cigarettes containing flavour alone

Participants wishing to join the TC arm will be asked to continue their usual daily smoking habits, however, they will be asked not to smoke more than 30 cigarettes per day. Participants in this group will be asked not to use electronic cigarettes for the four week period of the trial.

For the groups receiving the electronic cigarettes, the Researcher or delegated individual will “dispense” the electronic cigarettes to participants. Instructions and explanation of how to use the electronic cigarettes will be given. Participants will be asked not to smoke tobacco cigarettes during the trial period.

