8 STATISTICS AND DATA ANALYSIS

8.1 SAMPLE SIZE CALCULATION

The primary endpoint measurement is change in brachial artery FMD, which is expressed as the maximum FMD percentage change from baseline. Based on our existing data for this measure (mean response 7.8%, SD=3.5%), and assuming mean FMD reductions of 2%, 1% and 0% in the EC-Nicotine-free, EC-Nicotine, and TC groups respectively with a SD of the change in FMD =3.0% (based on our previous study³¹), and a using a sample size calculation using Linear Contrast Tests³⁷ a sample size of 36 subjects in each group will have 80% power to detect an improvement in FMD of 2.0% and 1.0% in the EC-nicotine-free and EC-nicotine groups respectively compared to the TC group at 5% significance. Assuming 10%, 15%, and 20% drop-out rates in the TC, EC-nicotine & EC-nicotine-free groups respectively, we will require 135 completed subjects. **All drop-outs will be replaced to achieve 36 completed subjects in each group.**

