5 STATISTICS AND DATA ANALYSIS

5.1 SAMPLE SIZE CALCULATION

The primary endpoint measurement is change in brachial artery FMD, which is expressed as the maximum FMD percentage change from baseline. Based on our existing data for this measure (mean response 7.8%, SD=3.5%), and assuming mean FMD reductions of 2%, 1% and 0% in the EC-Nicotine-free, EC-Nicotine, and TC groups respectively with a SD of the change in FMD =3.0% (based on our previous study[1]), and a using a sample size calculation using Linear Contrast Tests[2] a sample size of 36 subjects in each group will have 80% power to detect an improvement in FMD of 2.0% and 1.0% in the EC-nicotine-free and EC-nicotine groups respectively compared to the TC group at 5% significance. Assuming 10%, 15%, and 20% drop-out rates in the TC, EC-nicotine & EC-nicotine-free groups respectively, we will require 135 completed subjects. All drop-outs will be replaced to achieve 36 completed subjects in each group to fulfil the explanatory nature of the trial.

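### The cap of 45 per arm conflicts with replacing drop-outs until each group has 36 completers, and the rules let one EC arm close before the other, leaving late EC entrants outside 1:1 randomisation

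*Protocol*

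**What the plan says.** **Stopping.** Protocol 5.5.1 sets it by arm: "Recruitment will stop when the required number is reached in each arm (maximum 45 per arm". It does not say whether the required number counts people enrolled or people who complete, or whether the two EC arms close together.

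**Replacement.** Protocol 8.1 sets it by group: "All drop-outs will be replaced to achieve 36 completed subjects in each group". SAP 5.1 repeats this and adds a reason: "All drop-outs will be replaced to achieve 36 completed subjects in each group to fulfil the explanatory nature of the trial". Neither says how a replacement is allocated.

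**Expected loss.** Protocol 4.1 states that "it is anticipated that the dropout rates will vary depending on which group they have been randomised to", and gives 10% for TC, 15% for EC-nicotine and 20% for EC-nicotine free.

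**Allocation.** Protocol 5.5.1: "Randomisation will be carried out in a 1:1 fashion for the 2 randomised arms via a centrally controlled web-based GCP compliant randomisation system", with minimisation on age, sex and pack years. Protocol 5.5.2: "Participants who wish to be randomised to one of the EC arms will be randomised to one of two groups in a 1:1 fashion". No exception is made for late entrants or replacements.

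**What is randomised.** Protocol 5.5.1: "The TC arm will not be randomised". The SAP summary still describes three randomised groups; I follow the Protocol here. The only randomised comparison is therefore EC-nicotine against EC-nicotine free, which Protocol section 2 lists as a secondary outcome: "Change in FMD between EC-nicotine and EC-nicotine free groups". Apart from the vascular measurements, the study is unblinded.

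**The concern.** Two arms with different expected losses, filled 1:1, will not usually reach a fixed number of completers together. Either one arm overshoots, which the cap limits, or one arm closes while the other stays open.

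Once a single EC arm is open, the next EC volunteer has only one possible allocation. Minimisation has nothing to balance, and an unblinded volunteer can accept or decline knowing the product. Such people would be analysed as if randomised. The primary analysis is per protocol (Protocol 8.3, SAP 6.2), so replacements who complete enter it directly, and no planned analysis identifies them.

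At stake is the integrity of the one comparison that randomisation protects. There is also a practical problem: when an arm has 45 entrants and fewer than 36 completers, one rule forbids a replacement and the other requires it.

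**Working it through.** **1. The plan's own figures.** Inputs from Protocol 8.1: mean changes of 2, 1 and 0 (EC-nicotine free, EC-nicotine, TC), SD of change 3.0, 80% power, 5% significance. With equal groups, the linear contrast (1, 0, −1) reduces to EC-nicotine free against TC:

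n = 2 × (1.960 + 0.842)² × 3.0² / 2² = 35.3, rounded up to 36 per group.

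Power at 36 is 80.7% by the normal formula and 80.0% by the t contrast on 105 df. The plan does not state sidedness; two-sided reproduces 36, one-sided gives 28. Inflating for drop-out: 36/0.90 = 40, 36/0.85 = 42.4 (43), 36/0.80 = 45. So 45 is the worst-arm figure applied to all arms.

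**2. Expected completers from 45.** TC 45 × 0.90 = 40.5; EC-nicotine 45 × 0.85 = 38.25; EC-nicotine free 45 × 0.80 = 36.0. The nicotine-free arm has no margin.

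**3. Can both rules be met?** Treating drop-outs as independent:
- EC-nicotine: P(Bin(45, 0.85) ≥ 36) = 0.873
- EC-nicotine free: P(Bin(45, 0.80) ≥ 36) = 0.588
- both: 0.873 × 0.588 = 0.513

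At least one EC arm is short at the cap with probability 1 − 0.513 = 0.487.

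**4. How many entrants would face one known arm, if arms close separately?** I simulated this with 3,000 runs per scenario. Minimisation was represented by a biased coin favouring the smaller arm with probability 0.8 (assumed). The delay before completion is known was set at 0 or 6 entrants (assumed). For scale, 90 EC entrants over 22 months is 4.1 a month, and four weeks plus ten days is 38 days or about 1.25 months, hence about 5 entrants.

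| Arm closes at | Mean affected | Share of EC entrants | 95th percentile |
|---|---|---|---|
| 45 enrolled | 1.3 | 1.5% | 3 |
| 36 completers, cap kept | 1.9 to 3.2 | 2% to 4% | 4 to 7 |
| 36 completers, no cap | 4.6 to 6.6 | 5% to 7% | 10 to 13 |

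Simple randomisation, which is not planned, would give means of about 7 to 11.

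**5. Possible effect on the estimate (illustration only).** If the affected entrants differ from the rest by 1 FMD point (assumed), 3 of 45 shift their arm mean by 3/45 × 1 = 0.07 points, and 10 of 45 shift it by 10/45 × 1 = 0.22. The planned EC-nicotine free against EC-nicotine difference is 2 − 1 = 1.0 point.

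**The case against.** The strongest reply is that the documents nowhere direct a replacement to a single arm. Protocol 5.5.2 promises 1:1 randomisation to everyone who chooses EC, allocation is central, and the stopping sentence can be read as ending recruitment only when all arms are full. This stands. A reader might infer that the plan sends late entrants to one arm; it does not say so. The rules permit it and leave the matter open.

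A reader might also take the chance that exactly one EC arm is short at 45 entrants, 0.412 × 0.873 + 0.127 × 0.588 = 0.434, as the chance that a one-arm top-up is needed. It is not: at that point the cap allows no top-up in either arm. It measures shortfall, not non-random allocation.

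Nor do the documents support a claim that the bias would favour the arm that lost most people, or that drop-outs could not tolerate their product. Reasons for drop-out are still to be ascertained (Protocol 8.3, SAP 5.3), and nothing fixes a direction.

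Finally, the affected randomised comparison is secondary, the primary contrast with TC is non-randomised by design, and FMD is read by a blinded operator. All true. But blinded reading protects the measurement, not who enters an arm, and a small expected number does not excuse leaving the allocation rule open in the only randomised comparison.

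**Conclusion.** The point holds as a conflict between two stated rules with an allocation gap attached. Under the plan's drop-out rates and independent drop-outs, the cap and the completer target can both be met in the EC arms only about 51% of the time.

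If the site then closes EC arms separately, an average of about 1 to 3 people with the cap, or 5 to 7 without it, would have a known allocation. These counts rest on the biased-coin stand-in for minimisation and the assumed delay. At that size the EC-nicotine versus EC-nicotine free comparison is weakened; to call it broken would go beyond the evidence. The size and direction of any bias are unknown. The change is still worth making, because it is cheap and protects the only randomised comparison.

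**What to change.** In Protocol 5.5.1 and 8.1 and in SAP 5.1:

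- Close both EC arms together when 90 people in total have been randomised, and remove the per-arm limit for these two arms.
- State that every replacement takes a new TRUsT allocation, 1:1 with minimisation, to either EC arm.
- State that the total of 90 governs over the target of 36 completers, and report the achieved precision if an arm ends slightly below 36.
- Flag anyone allocated while only one EC arm was open, and omit them in a sensitivity analysis of EC-nicotine versus EC-nicotine free.

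**Cost.** Wording, a setting in the randomisation system, and possibly a few completers in one arm. With 45 entrants the nicotine-free completers have SD √(45 × 0.80 × 0.20) = 2.7 around 36. If that arm ended at 32 and TC at 40, the standard error of the primary contrast would be 3.0 × √(1/32 + 1/40) = 0.71. Then 2/0.71 = 2.81, and power is Φ(2.81 − 1.96), about 80%.

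**Alternative.** If the sponsor prefers the completer target to govern, both EC arms can stay open at 1:1 until each has 36. That needs about 91 EC entrants on average, with a 95th percentile of 51 per arm, and the cap of 45 would have to go.

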5.5.2 Intervention Allocation

Participants will initially be asked if they wish to continue smoking TC or if they would like to be randomised to one of the EC arms. Participants who wish to be randomised to one of the EC arms will be randomised to one of two groups in a 1:1 fashion. The groups will be:

- a) Switch to electronic cigarettes containing nicotine plus flavour
- b) Switch to electronic cigarettes containing flavour alone

Participants wishing to join the TC arm will be asked to continue their usual daily smoking habits, however, they will be asked not to smoke more than 30 cigarettes per day. Participants in this group will be asked not to use electronic cigarettes for the four week period of the trial.

For the groups receiving the electronic cigarettes, the Researcher or delegated individual will “dispense” the electronic cigarettes to participants. Instructions and explanation of how to use the electronic cigarettes will be given. Participants will be asked not to smoke tobacco cigarettes during the trial period.

5.5.3 Withdrawal procedures

When participants withdraw from active treatment the study team will ask them if they are willing to remain in the study and complete the study assessments.

If participants withdraw from the study and do not wish to return for study visits, contact with them will be maintained by the PI, trial manager, researcher or research assistant to ensure resolution of adverse event(s). If withdrawal is due to an AE it will be logged as such on the Adverse Event Log.

Participants are free to withdraw from the study at any time. The reasons, if known, will be recorded in the medical casenotes and CRF. Although a participant is not obliged to give reason(s) for withdrawing prematurely, if the participant appears lost to follow up, the CI will make a **reasonable** effort to ascertain the reason(s), while fully respecting the individual’s rights, and will demonstrate that everything possible was done in an attempt to find any participant lost to follow-up. Those lost to follow-up or withdrawn will be identified and a descriptive analysis of them provided, including the reasons for their loss and its relationship to treatment and outcome.

6 STUDY & SAFETY ASSESSMENTS

See Study Matrix, Section 3.3.

Flow Mediated Dilatation

Participants will be asked to fast from midnight the night before their visits, with the visit being performed in the morning. Participants who are electing to take part in one of the 2 randomized arms will also be asked not to smoke for 4 hours prior to their visits. Participants electing to take part in the tobacco cigarette arm do not have to withhold cigarettes for 4 hours but they will be asked to keep their smoking practises consisted before both visits. Endothelial function will be measured non-invasively at 0 and 1 month using the standard technique of flow mediated dilatation (FMD) of the brachial artery in response to hyperemia and to sublingual GTN. Brachial artery diameter and flow are determined by M mode and Doppler ultrasound as described by us previously³¹. FMD measurements are represented as change in arterial diameter from baseline. We will follow established protocols³². FMD is the technique we used recently to show a beneficial effect of allopurinol on endothelial function in subjects with chronic kidney disease³³ and in coronary artery disease³⁴. Our in house CV for FMD measurements is 3%. The FMD will be measured by a single experienced operator who will be blinded to treatment arms.

Vascular Stiffness

Pulse wave velocity (PWV) and pulse wave analysis (PWA) measurements including augmentation index corrected for heart rate (Aix@75) will be performed at baseline and 4 weeks using Sphygmocor™ as previously detailed³⁵. The FMD, PWV and PWA will be measured by a single experienced operator who will be blinded to treatment arms. These two measures have been validated as markers of cardiovascular risk³⁶.

Blood tests

The following blood tests will be carried out:

- 1) Oxidised LDL
- 2) High-sensitivity CRP
- 3) Platelet reactivity
- 4) Peripheral blood mononuclear cells for Oxidative stress NRf2 expression only (30 patients only, to be randomly selected).

Blood will also be stored, with patient consent, for future biomarker analysis.

